## **2 TRIAL DESIGN**

This is a multicentre, two parallel-arm, open label, individually randomised pragmatic trial with a nested pilot trial.

Potential participants who met the eligibility criteria were identified during a search of their electronic health records at their general practice. The electronic search criteria were developed centrally by the research team in partnership with TPP and made available for running locally on SystmOne e.g. by practice managers, Local Clinical Research Network (LCRN) Research Nurse Team, or Leeds CCG Pharmacy Technician team. Potential participants were sent an invitation pack and those interested in taking part returned an expression of interest form to the trial team. They were telephoned and booked into an either a face to face, or telephone appointment with their GP or Research Nurse at a time that was convenient to them. During this appointment, their GP or a delegated member of the staff confirmed their eligibility to participate and consented them to take part in the trial. The participants then received another telephone call from a member of the trial team to complete the baseline case report form (CRF). At this point, the participants were asked if they had taken any antibiotics in the previous two weeks; if they had, the randomised/baseline call will be postponed until the participant has been free of antibiotic use for two weeks.

Once the baseline CRF was complete the participants were randomised to usual care or the PAAP intervention arm. Those randomised to the PAAP intervention arm were booked into an appointment at the clinic where they had penicillin allergy testing.

Participants recruited during the nested pilot phase were followed up for an initial 4 months for the feasibility outcomes, during which they were contacted monthly by the trial team. Following a “stop go” assessment, all nested pilot study participants were subsequently followed up for at least 12 months in the main trial to align their follow-up with participants recruited to the main trial.

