Not all patients will have an eligible antibiotic prescription for an infective episode during the follow-up period, and not all episodes will generate analysable data. We have allowed for 50% patients not contributing any data to the primary outcome.

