## **9 SAFETY ANALYSIS**

All participants randomised will be included in the safety analysis. The safety analysis will be conducted on an as treated (AT) basis, participants will be analysed by the intervention they actually received instead of the intervention they were randomised to receive. The safety analysis will be conducted on the AEs and SAEs as appropriate.

Safety of the trial participants is paramount. Consequently, PAAP testing is performed in a hospital clinic to mitigate any risk of dealing safety and swiftly with anaphylaxis or other serious reaction to the oral challenge test, this is standard care in hospital clinics where suitably qualified and trained personal and equipment are at hand. Access details to the on-call immunology staff are given to all participants as is this standard of care for all penicillin-allergy assessments to ensure appropriate management of problems that might develop after the participants return home.

Telephone calls by the research team at the following time-points collected information on adverse events (AEs) associated with the penicillin allergy test (skin test and/or oral challenge test): 4-6 days, and 28-30 days after penicillin allergy testing.

Adverse events occurring up to 28 days after an antibiotic prescription from their general practitioner for any pre-defined infections listed in the protocol is captured through the participant diary and telephone calls by the research team after the start of an antibiotic prescription.

The frequency of adverse events (AEs) and adverse reactions (ARs) will be summarised. A list of all adverse events and reactions experienced during the trial will be presented including information on the type of event, AE description, start date of AE, end date of AE, severity of the event, outcome of the AE, event related to treatment, what the adverse reaction was too, description of AR, what test the participant had (skin/OCT/both), and whether or not the participant went on to be de-labelled as being allergic to penicillin. Participants that went on to be de-labelled will be highlighted in the table of adverse events.

In addition to summarising all adverse events and reactions, only those that occurred during 3 days post antibiotic follow-up will be presented.

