If the list and description of the adverse events could potentially unblind the report, this will not be presented in the blinded version of the report, only the summary statistics will be provided. In this case the detailed list of adverse events will only be presented in the unblinded report, which will only be prepared when the blinded report has been signed off.

A serious adverse event (SAE) is any untoward medical occurrence that:

- Results in death,
- Is life-threatening,
- Requires inpatient hospitalisation or prolongation of existing hospitalisation,
- Results in persistent or significant disability/incapacity,
- Or consists of a congenital anomaly or birth defect.

Other important medical events' may also be considered serious if they jeopardise the participant or require an intervention to prevent one of the above consequences.

- Anaphylaxis to an antibiotic will be considered an SAE as part of the ALABAMA trial.

NOTE: The term "life-threatening" in the definition of "serious" refers to an event in which the participant was at risk of death at the time of the event; it does not refer to an event which hypothetically might have caused death if it were more severe.

The number and percentage of participants experiencing at least one SAE will be reported by the intervention they received (rather than the intervention they were randomised to receive) and will be analysed using a Fisher's Exact test if possible. The total number of SAEs per AT group will be reported for each serious adverse event. The total number of SAEs per AT group will also be reported.

Any SAEs identified during the ALABAMA trial need to be assessed for their relatedness to:

1. Penicillin Allergy Assessment (PAA)
2. An antibiotic prescription\* for any of the pre-defined infections listed in Appendix G of the protocol and Appendix II of this document.

\*Because patients may have more than one antibiotic prescription during the ALABAMA trial, the relatedness of SAEs was assessed in relation to their most recent antibiotic prescription for any pre-defined infections.

SAE description, start date of SAE, stop date of SAE, severity of the event, reason the event was classified as serious, event related to intervention, was the event unexpected, outcome of the SAE, allocated intervention group, and received intervention, will be reported for each serious adverse event.

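### The SAE test in section 9 compares as-treated groups that are neither observed alike nor formed by randomisation

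*SAP*

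**What the plan says.** Section 9 puts the whole safety analysis, AEs and SAEs, on an as-treated basis. For SAEs: "The number and percentage of participants experiencing at least one SAE will be reported by the intervention they received". That proportion "will be analysed using a Fisher's Exact test if possible". No common observation period is set and no allowance is made for time under observation.

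The section describes two streams of safety contact:

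- After the test: "Telephone calls by the research team at the following time-points collected information on adverse events (AEs) associated with the penicillin allergy test". The calls fall at "4-6 days, and 28-30 days after penicillin allergy testing".
- After antibiotics: "Adverse events occurring up to 28 days after an antibiotic prescription from their general practitioner for any pre-defined infections listed in the protocol" are captured by diary and calls. This stream is open to both arms.

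Appendix IV schedules AEs and SAEs in a single row. Its columns are shifted in the text available, but its eight marks fit the test visit, two post-test calls, three nested-pilot calls and two post-antibiotic calls, with none at the 12-month contact. Section 2 says of nested-pilot participants that they had an initial 4 months of follow-up, "during which they were contacted monthly by the trial team".

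Section 3.3 defines the as-treated groups. PAAP is everyone allocated to it who had a skin test or oral challenge; usual care is everyone else, including untested PAAP participants. Section 6.4 allows for PAAP being delivered more than 90 days after randomisation.

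**The concern.** A between-group test of the proportion with an SAE is interpretable only if an SAE has the same chance of being found in each group, and if group membership does not depend on what happened after randomisation. Neither condition is secured here.

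On ascertainment, a tested participant has about a month of scheduled safety contact with no counterpart in usual care. A main-trial usual-care participant with no listed antibiotic episode appears to have no scheduled safety contact at all. If SAEs come to light mainly through contacts, PAAP will show more of them without being more harmful.

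On grouping, testing happens after randomisation, sometimes long after. Sorting people by whether they were eventually tested lets early events decide, or be misattributed to, a group.

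At stake is the only formal test of SAEs as a whole. A small P-value could reflect the contact schedule, and a large one could hide a difference that the grouping rule has offset. No primary or secondary efficacy conclusion depends on it.

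**Working it through.** **1. Group size.** The plan gives no figure for the SAE comparison, so the sample size in section 2.3 supplies the group size. For 4% v 14%, two-sided 5% and 90% power, the two-proportion formula gives 171 per arm without and 190 with continuity correction. Then 190 / 0.9 = 211.1, rounded up to 212; 212 / 0.5 = 424 per arm; total 848. This matches the plan.

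**2. Inputs.**
- Post-test window: 28 days, tested participants only (section 9).
- Post-antibiotic window: 28 days, either arm (section 9).
- Half of participants have one such window. Section 2.3 assumes 50% will need a prescription within a year: "We have allowed for 50% patients not contributing any data to the primary outcome".
- Assumed, because the SAP gives no figure: a 12-month SAE risk R of 10%, 20% or 30%, equal in both groups; a share q of time outside the windows in which an SAE would still be found.
- Simplifications: constant hazard, all PAAP participants tested, no overlapping windows, no nested-pilot contacts.

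**3. Days under active observation.** Usual care: 0.5 x 28 = 14. Tested PAAP: 28 + 14 = 42. Ratio 3. Without a prescription the figures are 0 and 28 days.

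**4. Probability of an observed SAE.** Daily hazard: λ = -ln(1 - R) / 365. With w window days, P(w) = 1 - exp(-λ[w + q(365 - w)]).
- Usual care: 0.5 P(0) + 0.5 P(28).
- Tested PAAP: 0.5 P(28) + 0.5 P(56).

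Example with R = 20% and q = 0: λ = 0.000611, P(28) = 0.0170, P(56) = 0.0337. Usual care is 0.0085 and PAAP 0.0253, a ratio of 2.98. With 424 per group, 3.6 v 10.7 participants are expected to have an observed SAE.

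**5. Rejection by Fisher's exact test.** Two-sided at 0.05, 424 per group, full enumeration, equal true risk:

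| Outside detection q | Observed ratio | R = 10% | R = 20% | R = 30% |
|---|---|---|---|---|
| 0 | about 3.0 | 12.8% | 38.2% | 62.4% |
| 10% | about 1.5 | 7.7% | 16.2% | 25.2% |
| 25% | about 1.2 | 5.4% | 8.2% | 11.8% |
| 50% | about 1.07 | 4.0% | 5.1% | 5.9% |
| 100% | 1.00 | 3.8% | 4.1% | 4.2% |

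Where the rate is raised, the rejections are almost all against PAAP. At R = 5% and q = 0 the rate is only 1.9%, because events are too few for the test to reject.

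**6. Grouping by dates.** This needs no arithmetic. Take a PAAP participant tested more than 90 days after randomisation, which section 6.4 anticipates. An SAE in those first 90 days counts as PAAP, though the test cannot have caused it. Take another who dies, or has an SAE that rules out the test. Section 3.3 moves that event to usual care. The second rule lowers the PAAP proportion, against the direction of step 5, and both rules operate even if every SAE is captured.

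**The case against.** The strongest reply is that the narrow windows in section 9 are worded for AEs. For SAEs the section speaks of any identified during the trial and lists no sources. SAE reporting routes are commonly set in the protocol, which is not shown. Section 2 says that all participants had case note review, with hospital episode and mortality data if required, and deaths and admissions, both SAE criteria, would show there. This stands. A reader might infer that SAEs were collected only around the test and after prescriptions; the SAP does not say so, and the nested-pilot contacts, apparently with AE/SAE collection, count against it. Equally, the SAP does not say that records feed the SAE count. Section 2.1.2.5 lists the SAE report separately from notes review, HES, ONS and SystmOne and provides for their disagreement, so it reads as a distinct stream.

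Second, arm-neutral safety evidence is already planned. Section 1.4.2 labels admissions and mortality as safety outcomes, sections 5.1 to 5.3 model them by randomised group, and section 8 repeats the admission analyses over all 12 months. This also stands. It would be wrong to infer that the trial cannot separate harm from contact schedule at all; for deaths and admissions it can.

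Third, as-treated grouping is a common convention for safety, and section 9 already lists each SAE with its start date, allocated group and intervention received. That makes repair easy, but it does not justify a P-value on groups shaped by events after randomisation.

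**Conclusion.** The point holds in a limited form. The SAP fixes a significance test on as-treated groups without a period or source common to both. Tested participants certainly have safety contacts that the comparator lacks, and the grouping certainly ignores dates.

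The size of the ascertainment bias is not known. It runs from a threefold spurious ratio, with 13% to 62% false rejection at assumed annual risks of 10% to 30%, through about 1.2 and 5% to 12% with a quarter of outside time covered, to near nominal at half coverage or more. The threefold figure is the extreme case, with nothing found outside the windows and every PAAP participant tested. It should not be quoted as the expected bias.

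The date problem remains with perfect capture, but its size cannot be computed from the SAP. Because it can act against the ascertainment bias, the net direction cannot be stated either. The reading of the AE/SAE row rests on a table with displaced columns and should be checked against the original layout.

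**What to change.** In section 9:

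- State the sources and the period from which SAEs are counted.
- Make the formal between-group comparison by randomised arm, over a period and from sources common to both arms. Deaths (section 2.1.2.5) and all admissions over 12 months (section 8) already meet most of this need and can carry it.
- Keep the as-treated SAE table as descriptive, without Fisher's test.
- Tabulate SAEs found at the clinic or at the post-test calls for tested participants only, without a P-value.
- Flag every SAE whose start date precedes the test date.

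The cost is SAP wording and programming: SAE start dates, allocation and treatment received are already due to be reported, and the record sources are already in use. The downside is that SAEs other than deaths and admissions leave the formal test and are reported descriptively.

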Regular reports were run in the ALABAMA unit to identify participants who had been prescribed an antibiotic, for any cause, in the previous 7 days. A member of the research team sent an alert to the trial research nurses team who then followed the participant up for the duration of the associated infection. The research team then designated an antibiotic prescription as a ‘primary event’ if the patient was prescribed an antibiotic for a pre-defined list of infections (see Appendix II). Participants receiving antibiotics for a primary event, were asked to complete a symptom diary. At the end of the follow up period their electronic health records were reviewed to ensure we had captured all antibiotic events. All trial participants had case note review and, if required had capture hospital episode statistics, and mortality data.

Throughout this process general practice staff and participants received behaviour change intervention materials.

See Appendix III for study flowchart.

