11. Cost effectiveness for the PAAP intervention compared to usual care	11. Self-report health/QoL outcome: EQ-5D-5L will be used a standardised instrument for measuring health outcome at baseline and 1 year. For those that receive antibiotics, EQ-5D-5L will be collected on day 2-4 and day 28-30 after antibiotic treatment. NHS health resource use will be measured through primary and secondary care notes review and linked HES data.	11. EQ-5D-5L will be used as a standardise instrument for measuring health outcome at baseline and 12 months post-randomisation and on day 2-4 and day 28-30 post-antibiotic episode (end point is 12 months post-randomisation). Costs will be measured at 12 months and, through model-based extrapolation, up to 5 years after randomisation
12a. Effect of PAAP on de-labelling at 3 months post-randomisation	12a. The proportion of ALABAMA participants whose labels are removed from the medical eHR record allergy section (primary care notes review)	12a. At 3 months post-randomisation
12b. Effect of PAAP on de-labelling up to 12 months post-randomisation	12b. The proportion of ALABAMA participants whose labels were removed and remain removed from the medical eHR record allergy section up to 12 months post-randomisation (primary care notes review)	12b. Up to 12 months post-randomisation
13. Safety outcomes (Exploratory Outcomes)	13. A descriptive analysis will be preformed looking at the safety of de-labelling in the intervention group	13. Up to 12 months post-randomisation
14. Effects of PAAP on all outcomes for follow-up past 12 months	14. Descriptive analysis using data captured in primary and secondary notes review CRF/SystmOne report	14. Until the end of the study

[figure not shown]

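### SAE relatedness and solicited AE capture are tied to antibiotics for the listed infections, so penicillin reactions after de-labelling can be misattributed (if serious) or under-ascertained (if not)

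*SAP*

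**What the plan says.** **SAE relatedness (SAP section 9).** "Any SAEs identified during the ALABAMA trial need to be assessed for their relatedness to" two things: the penicillin allergy assessment, and an antibiotic prescription "for any of the pre-defined infections listed in Appendix G of the protocol and Appendix II of this document". A footnote deals with participants who had several courses: "the relatedness of SAEs was assessed in relation to their most recent antibiotic prescription for any pre-defined infections". The same section makes anaphylaxis to an antibiotic an SAE, with no limit by indication.

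**AE capture (SAP section 9).** After testing, calls are made at "4-6 days, and 28-30 days after penicillin allergy testing". After antibiotics, "Adverse events occurring up to 28 days after an antibiotic prescription from their general practitioner for any pre-defined infections listed in the protocol is captured"; the means are the diary and research-team calls.

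**Detection of prescriptions (SAP section 2).** Regular reports were run to "identify participants who had been prescribed an antibiotic, for any cause, in the previous 7 days". Each alert led to nurse follow-up of the associated infection, and records were reviewed at the end of follow-up for all antibiotic events. The symptom diary was for primary events only.

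**The objective served (SAP Appendix I, objective 13).** "A descriptive analysis will be preformed looking at the safety of de-labelling in the intervention group", with a timepoint of up to 12 months after randomisation and no restriction by infection.

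**The concern.** The Appendix II list defines the setting for the efficacy endpoint: infections for which a penicillin is first line. Whether a reaction was caused by a penicillin does not depend on why the penicillin was given. De-labelling, as defined in sections 2.1.2.8 and 2.1.2.9, removes the allergy entry from the primary care record. It does not remove it for some infections and keep it for others, so a de-labelled participant may be given penicillin for an indication off the list.

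A reaction to penicillin in someone whose label was removed is the harm most specific to this intervention. If the relatedness rule cannot point to the drug that was taken, or if reactions are solicited only after some courses, the description under objective 13 rests on incomplete attribution and ascertainment.

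**Working it through.** No arithmetic settles this. The check is to take the section 9 rules as written and follow a penicillin reaction in a de-labelled participant through them.

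| Course before the reaction | Antibiotic used as SAE relatedness reference | Diary/call AE capture stated in section 9 |
|---|---|---|
| 1. GP penicillin, listed infection, no switch | That penicillin | Yes |
| 2. Hospital penicillin, listed infection | That penicillin (the relatedness rule is not limited to GP prescribing) | No |
| 3. GP penicillin, listed infection, then a switch to another drug for it, then a delayed reaction | The second drug | Yes |
| 4. Penicillin, unlisted indication, with an earlier listed prescription | The earlier drug, whatever it was | No |
| 5. Penicillin, unlisted indication, no listed prescription | None; only the allergy assessment remains | No |

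Only the first case works on both counts.

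- **Case 3 was foreseeable.** Section 2.3 records that the initial sample size assumed re-prescription of an alternative antimicrobial within 28 days at 19.8% under usual care and 11.9% under PAAP. Those are planning figures, not observed rates. They do show that a second drug inside the plan's own AE window was expected.
- **Cases 4 and 5 are possible.** Appendix II does not cover every reason for an antibiotic; urinary infection, for example, is absent.
- **Case 2 separates efficacy from safety.** Section 2.1.1 counts a penicillin found in hospital prescribing reports towards the primary outcome, while the stated post-antibiotic AE capture covers GP prescriptions only.

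Two further comparisons within the SAP:

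- **Event definition against causality rule.** Anaphylaxis to any antibiotic is an SAE, but its causality is tested only against antibiotics for listed infections.
- **Section 2 against section 9.** Section 2 has alerts and nurse follow-up after antibiotics for any cause. Section 9 states capture for the pre-defined infections only, and Appendix IV ties the post-antibiotic calls to episodes of trial relevance. These do not agree on which prescriptions lead to AE follow-up.

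**Direction.** An individual misattribution can go either way; in case 4 the earlier drug might itself have been a penicillin. But a reaction to an unlisted course can never be matched to that course, and a non-serious one is not solicited. Both reduce the number of reactions seen after de-labelling.

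**The case against.** The strongest reply is that most of the safety analysis does not depend on these rules.

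- All SAEs identified are counted. The comparison of participants with at least one SAE (Fisher's exact test, if possible) is made by treatment received and does not use relatedness. This stands. A reader might infer that serious reactions to unlisted courses go uncaptured; section 9 does not support that. For SAEs the gap is one of attribution.
- All AEs and reactions are to be listed with what the reaction was to and whether the participant was de-labelled. Section 2.1.2.9 counts re-labelling by arm, and admissions over the full 12 months are analysed as exploratory. These are real safeguards, but partial ones. The listing can show only what was ascertained, and a re-labelling count names neither a reaction nor a drug. The fields for the SAE listing include relatedness to the intervention but, unlike those for AEs, not the agent.
- Any-cause alerts and record review may pick up non-serious reactions. This also stands in part, so under-ascertainment is the fair word, not omission.
- Safety procedures usually sit in the protocol, which was not available for this check, and the footnote is in the past tense. But the SAP states these rules itself and should state them consistently.
- Nothing in section 9 excludes unlisted courses from objective 13. That is correct, so there is no outright contradiction. Section 9 nevertheless gives the objective neither an exposure denominator nor a matching relatedness category.

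A reader might also try to size the gap by applying the planned 14% to all 424 PAAP participants (424 × 0.14 ≈ 59 exposed). The plan's own adjustments do not support that. With 50% needing a prescription and 10% attrition, 424 × 0.5 × 0.9 ≈ 191 are evaluable, and 191 × 0.14 ≈ 27. Either figure describes listed infections only and says nothing about courses off the list.

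**Conclusion.** The point holds as a gap in attribution and ascertainment. As written, a serious reaction to penicillin given for an unlisted indication, or a delayed reaction after a switch, can be judged against the wrong drug or against no antibiotic. Non-serious reactions to unlisted or hospital courses may be under-recorded. This weakens objective 13 in the direction that favours de-labelling.

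The overall SAE counts and their comparison are unaffected. It therefore does not follow, as a reader might conclude, that the whole safety conclusion is biased.

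The size cannot be computed: the SAP gives neither the share of penicillin courses outside Appendix II nor any reaction rate. The conclusion assumes only that some de-labelled participants receive penicillin off the list or change drug within an episode, and that the protocol does not already set a wider rule. The matter should be corrected before safety results are reported, but it does not threaten the trial's main analysis.

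**What to change.** - **Relatedness.** In the section 9 analysis, assess and report each SAE against the allergy assessment and against every antibiotic received in the 28 days before the event, for any indication and any prescriber. The 28 days is the plan's own AE window.
- **SAE listing.** Add the suspected agent, as the AE listing already has.
- **Objective 13.** Tabulate events after any penicillin course following de-labelling, with all such courses as the denominator. Take them from the any-cause SystmOne reports, the notes review and, where available, the hospital prescribing reports.
- **Consistency.** Reconcile sections 2 and 9 and Appendix IV on whether AE follow-up after an antibiotic covers any-cause or only pre-defined prescriptions.

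The cost is a SAP amendment, or a deviation justified in the final report as section 1.2 allows, plus a fresh causality judgement for a few SAEs. That is more than re-coding, because a new assessment is needed. One limit remains: non-serious events after unlisted courses already completed will come mainly from records, not diaries or calls, and the report should say so.
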